#### **4.7 DISCONTINUATION OF SUBJECTS FROM STUDY**

Subjects must discontinue study treatment and withdraw from the study or optional sub-study for any of the following reasons:

- Withdrawal of informed consent (subject's decision to withdraw for any reason)
- PCa relapse at any time after completion of PROSTVAC administration (see 7.5 for definition)
- Any clinical adverse event (AE), laboratory abnormality, or intercurrent illness which, in the opinion of the investigator, indicates that continued participation in the study is not in the best interest of the subject
- Termination of the study by BNI
- Loss of ability to freely provide consent through imprisonment or involuntarily incarceration for treatment of either a psychiatric or physical (e.g., infectious disease) illness
- Initiation of any form of non-protocol cancer treatment
- Initiation of scheduled narcotics for pain treatment

- Unacceptable toxicity defined as any grade 3-4 possibly or definitely related non-hematologic toxicity that does not improve to grade 1 or resolve within 28 days or any possibly or definitely related grade 3-4 hematologic toxicity that does not improve to grade 1 or resolve with 14 days.

General or specific changes in the patient's condition render the patient unacceptable for further treatment in the judgment of the investigator.

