## 7.3 OFF-STUDY ASSESSMENTS

Off study assessments will consist of those procedures indicated for day 730 if the patient's participation ends at that time, or at any earlier time. These include:

- clinical examination (history and physical examination);
- assessment of toxicity or adverse events;
- CBCD;
- CMP
- bone scan and CT scan of abdomen, and pelvis (a Prostascint scan or MRI of abdomen, pelvis can be substituted). Scans will not be repeated at the off-study point if they have been performed in the preceding 2 months.
- PSA;

- total testosterone;
- research assessments
  - Blood samples-See Section 8 for details
  - Quality of Life questionnaires

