## 8 CORRELATIVE STUDIES

### 8.1 RESEARCH BLOOD COLLECTIONS

A variety of analyses will be performed on the research blood samples collected for this study. To evaluate biological responses to vaccinations, plasma, serum, as well as whole blood samples will be collected from all enrolled subjects. Plasma will be analyzed for the development of antibodies to the vaccinia and fowlpox virus vectors, the PSA insert, other prostate specific antigens, as well as tumor associated antigens. Serum will also be profiled for changes in cytokine and chemokine expression and circulating tumor markers. Immune function analysis will be performed by isolation of PBMCs for immune function assays. PBMCs will be evaluated for PSA antigen-specific responses by ELISPOT and flow cytometric-based methods. Determinant spreading to other prostate antigens and tumor-associated antigens will also be examined. All evaluations will be performed at laboratories using standardized procedures. Subject samples may be kept for up to one year past the end of the trial for assay development, implementation, and data review. These described analyses will generate a large dataset that will potentially enable the identification of new biomarkers of disease prognosis and/or vaccine response.

Research assessments will not be made in real time, since they will require analyses that will be performed only in “batch mode” when samples are available. Research samples will be collected as indicated and stored for future assays, in accordance with MUSC and VAMC policies.

All patients will be expected to provide blood for research purposes per the timepoints outlined within the study calendar (Appendix A). Each research blood collection will require 38mL of anticoagulated peripheral whole blood.

Research Blood Collection Timepoints	At each blood collection, collect the following	
	Amount of Blood	Tube type
Baseline Day 85 Day 225 Day 730 or off study	10 mL	sodium heparin tube
	7 mL	lithium heparin tube
	21 mL (three 7 mL tubes)	EDTA tube
	7mL	Blood (clot) tube

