Descriptive statistics will be summarized for the AL measurements (e.g. median) at each time point (baseline, day 85, day 225, and day 730 or off study) for the entire patient population and for each racial group. We will compare the mean difference between two consecutive time points between two racial groups using a Wilcoxon rank sum test. A linear mixed model will also be fitted in which we will regress AL measurements on racial group, time, stress reactivity (may consider interaction terms) to explore the AL response profile difference. The outcome of RFS will be evaluated using Kaplan-Meier estimates and the statistical significance of difference in RFS between racial groups will be tested by a logrank test. In addition, a cox regression model will be explored.

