**APPENDIX A: SCHEDULED PROCEDURES AND ASSESSMENTS**

		Days on study f														
Therapeutic trial procedures	Procedure c	Pre a	1 n	15	29	57	85	113	141	225	309	393	477	561	645	730 g
	Informed Consent	X c														
	Full Physical Exam	X														
	Focused Physical Exam															
	Full Medical History	X														
	Interim Medical History o															
	AE assessment															
	CBCD	X														
	CMP	X														
	PSA	X m														
	Testosterone	X														
	CRP	X														
	Lipid Panel															
	CT (abdomen/pelvis)	X b														
	Tc-bone scan	X b														
	HIV test	X i														
	Hep B and C testing	X i														
Treatment	PROSTVAC-V															
	PROSTVAC-F															
Correlative Research	FACT-P															
	AUA															
	SHIM															
	Social Determinants Questionnaire															
	Research blood e															
	Research FFPE tissue	X i														
	Optional Sub-study Consent	X d														
Optional Sub-Study	Trier Stress Test	X i														

- a. Screening Assessments ("Pre") may be done up to 30 days prior to registration unless otherwise noted.
- b. Radiographic assessments may be done up to 26 weeks prior to registration. PSA at screening is required to document eligibility for post-operative PSA and may be done greater than 30 days prior to registration.
- c. The informed consent for the main study can be obtained more than 30 days prior to registration but must be obtained before any research procedures are completed
- d. The optional sub-study consent must be obtained prior to conducting the Trier Stress Test. The optional sub-study is voluntary and does not impact the patient's ability to participate in the main therapeutic portion of the trial.
- e. See [section 8](#) for blood draw volume and tube type requirements.
- f. all specified times are +/- 7 days
- g. or off-study day
- h. follow up will begin after the last day of study drug administration.
- i. Research blood, social determinants questionnaire and quality of life questionnaires may be completed any time after informed consent is signed and prior to Day 1 drug administration.

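### Aim 3 files samples drawn when a man leaves early under the same time point as Day 730, so the last allostatic-load change mixes intervals and disease states and could, under further conditions, differ by race for that reason

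*Combined protocol and SAP*

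**What the plan says.** - **Section 10.3, Aim 3.** AL is summarised at four time points, of which the fourth is Day 730 and off-study combined: "at each time point (baseline, day 85, day 225, and day 730 or off study) for the entire patient population and for each racial group". The test on changes is then: "We will compare the mean difference between two consecutive time points between two racial groups using a Wilcoxon rank sum test". A linear mixed model of AL on racial group, time and stress reactivity follows. The same paragraph tests RFS by race with a logrank test.
- **Section 8.1.** The research blood schedule uses the same combined label: "Baseline Day 85 Day 225 Day 730 or off study".
- **Section 7.3.** Off-study assessments are the "procedures indicated for day 730 if the patient's participation ends at that time, or at any earlier time", and they include the research blood.
- **Appendix A, footnote g.** The Day 730 column is marked "or off-study day".
- **Section 4.7.** "Subjects must discontinue study treatment and withdraw from the study or optional sub-study for any of the following reasons". The list includes relapse once vaccination is complete, withdrawal of consent, related severe toxicity that does not settle, and "Initiation of any form of non-protocol cancer treatment".
- **Section 10.1.** Men who only stop treatment and wish to stay are followed to 24 months, so they need not become early leavers.

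Section 10.3 has no rule that separates off-study samples, uses the actual sampling day, or takes account of relapse or new therapy.

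**The concern.** A change score compared between groups should cover the same span and the same kind of state in every man. Here the last change (Day 225 to the final sample) is a two-year follow-up value in one man and a value at relapse or withdrawal in another. The second kind may be drawn after other prostate cancer treatment has begun.

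Relapse is common in this population, and Aim 3 itself asks whether it differs by race. If it does, the two racial groups will differ in the share of early samples and in mean elapsed time. A resulting gap in AL change could then be read as a racial difference in stress biology when it reflects when, and in what condition, the men were sampled.

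**Working it through.** **No plan figure to reproduce.** The protocol gives no power, effect size or standard deviation for Aim 3. The RFS values below are its design assumptions from section 10.1: 0.60 (null) and 0.78 (target).

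**Step 1: is the pooling really stated?** Sections 8.1 and 10.3 and Appendix A footnote g give one label to Day 730 and off-study. Section 7.3 places the off-study draw on whatever earlier day participation ends. Section 4.7 makes relapse and new cancer therapy reasons to leave. Read together, a relapsing man's exit sample is summarised with true Day 730 samples. This is a stated rule, not a missing detail.

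**Step 2: the interval.** Completer: 730 − 225 = 505 days. Man leaving at the Day 309 visit: 309 − 225 = 84 days.

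**Step 3: how many final values could be early.** Expected relapse exits = N × (1 − RFS).
- N = 30: 30 × 0.22 = 6.6; 30 × 0.40 = 12.0.
- N = 33 (enrolled): 33 × 0.22 = 7.3; 33 × 0.40 = 13.2.
- Sub-study consenters at 70% to 80% of 33 (23 to 26 men): 23 × 0.22 = 5.1; 26 × 0.40 = 10.4.

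These are ceilings for relapse, because they assume every leaver gives blood. Other withdrawals would add to them.

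**Step 4: when does this create a racial difference?** Write the last change as noise (SD 1) + shift (if relapsed) + drift × days/505, with no true race effect. For groups A and B the expected difference, B minus A, is

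shift × (RFS_A − RFS_B) + drift × (mean days_B − mean days_A)/505.

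With exponential relapse over the 505 days, mean days = 505 × (1 − p)/(−ln p), where p is RFS. This gives 425 days at p = 0.70 and 364 at p = 0.50. With a shift of 1, the difference is 1 × (0.70 − 0.50) = 0.20 SD. With a drift of 1, it is (364 − 425)/505 = −0.12 SD.

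Simulated two-sided 5% rank-sum test, 4,000 runs per setting:

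| RFS, A vs B | Shift (SD) | Drift (SD) | Spurious difference (SD) | Rejection, 12 per race | Rejection, 18 per race |
|---|---|---|---|---|---|
| 0.60 vs 0.60 | 1 | 0 | 0 | 5.0% | 4.7% |
| 0.70 vs 0.50 | 0 | 0 | 0 | 5.0% | 4.4% |
| 0.70 vs 0.50 | 1 | 0 | 0.20 | 6.2% | 8.4% |
| 0.70 vs 0.50 | 0 | 1 | −0.12 | 5.4% | 6.1% |
| 0.78 vs 0.45 | 0 | 0 | 0 | 4.8% | 4.7% |
| 0.78 vs 0.45 | 1 | 0 | 0.33 | 10.5% | 14.4% |
| 0.78 vs 0.45 | 0 | 1 | −0.20 | 6.9% | 7.5% |

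The RFS values by race, the shift and the drift are assumptions, since the documents give none of them. The simulation applies each RFS over the 505 days from Day 225 and assumes that every man has both samples. Distortion appears only when relapse differs by race **and** AL depends on relapse or elapsed time.

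**The case against.** Several counter-arguments have force.

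- **Unequal relapse is not enough.** A reader might infer that any racial difference in relapse by itself produces a racial difference in AL change. The documents do not support that, and the zero-shift, zero-drift rows refute it. The further condition is plausible: section 2.6.2 presents AL as a marker of the bodily impact of stress, section 8.6 includes BMI in it, and section 2.2.2 lists increased body fat among the effects of androgen deprivation. But no section says that AL moves with time, relapse or therapy.
- **The count is a ceiling.** Appendix A footnote p lets non-local men be followed locally or by phone with only a PSA, so some leavers will give no blood. Men who leave before Day 225 have no Day 225 value. One might infer that their change would run from Day 85, but section 10.3 does not say so. The natural reading is that they have no Day 225-to-final difference.
- **The mixed model may be partly sound.** One might infer that its time term is the visit label, but the plan says only time. Actual days would deal with unequal intervals, though not with an effect of relapse or therapy.
- **Keeping only Day 730 ± 7 day samples is not a clean cure.** It selects men who stayed relapse-free and on study. It may also drop completers: follow-up runs two years from surgery (section 4.1), the calendar counts days on study, and treatment may start up to 120 days after surgery. Two post-surgical years could therefore end near study day 730 − 120 = 610.
- **A separate limit remains.** AL includes total and HDL cholesterol (section 8.6), but section 7.1 takes the lipid panel only at baseline. The full score is therefore not available at later visits as written, and relabelling samples does not change that.
- **Consequence is low.** Section 10.3 describes exploration, section 2.6.2 disclaims power for subtle racial differences in stress response, and the logrank test by race would help expose unequal relapse.

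All of this limits the size and certainty of the effect. None of it removes the stated pooling.

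**Conclusion.** The point holds in a limited form. The descriptive summaries and the rank-sum test, as written, combine scheduled final values with values taken at relapse, new therapy or withdrawal. The early share from relapse alone is at most about 22% to 40%, given the protocol's RFS range and blood from every leaver. Bias in the racial comparison is conditional, not automatic. Under the assumed 1 SD shift at relapse it is about 0.20 SD with RFS 0.70 vs 0.50, and about 0.33 SD with the wide gap of 0.78 vs 0.45. For the mixed model the issue depends on how time is coded. This is an inexpensive improvement to an exploratory analysis, and no decision rule rests on it.

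**What to change.** In section 10.3, Aim 3:

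1. Label and tabulate off-study samples separately from scheduled final-visit samples, by reason for leaving and by whether they were drawn after new prostate cancer therapy began.
2. State that time in the mixed model is the actual sampling day counted from first dose.
3. Report the Day 225-to-final rank-sum comparison both with and without early off-study samples. Do not replace it by a Day 730 ± 7 day restriction alone.
4. When reporting the version without early leavers, state that it is selected on staying relapse-free and on study.

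Cost: SAP wording and one extra sensitivity analysis, with no new visits or samples. It needs dated samples and therapy start dates; the Appendix D phone guide already asks for the latter. The version without early leavers will have fewer men.

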### **10.4 POPULATIONS FOR ANALYSES**

Subjects evaluable for toxicity or efficacy will be those who receive at least one dose of PROSTVAC-V.

## 10.5 ADDITIONAL ANALYSES

Demographic and clinical parameters will be tabulated. Critical parameters to be recorded include age at time of surgery, date of surgery, race, primary Gleason score, secondary Gleason score, pathologic stage, surgical margin status, extraprostatic extension status, seminal vesicle status, lymph node status, pre-operative PSA level, post-operative PSA level (> 6 wks after surgery). Formalin-fixed paraffin-embedded tissue from the prostatectomy specimen will be archived for future “omic” analyses to correlate with RFS.

## 11 ETHICAL CONSIDERATIONS

### 11.1 GOOD CLINICAL PRACTICE

This study will be conducted in accordance with GCP, as defined by the International ICH and in accordance with the ethical principles underlying the US CFR, Title 21, Part 50 (21CFR50). The study will be conducted in compliance with the protocol. The protocol, any amendments, and the subject informed consent will receive IRB approval before initiation of the study.

All potential serious breaches must be reported to the institutional IRB and DSMC. A serious breach is a breach of the conditions and principles of GCP in connection with the study or the protocol, which is likely to affect, to a significant degree, the safety or physical or mental integrity of the subjects of the study or the scientific value of the study.

Study personnel involved in conducting this study will be qualified by education, training, and experience to perform their respective tasks. This study will not use the services of study personnel where sanctions have been invoked or where there has been scientific misconduct or fraud (e.g., loss of medical licensure; debarment). Systems with procedures that ensure the quality of every aspect of the study will be implemented.

### 11.2 INSTITUTIONAL REVIEW BOARD

Before study initiation, the investigator must have written and dated approval/favorable opinion from the IRB for the protocol, consent form, recruitment materials, and any other written information to be provided to subjects. The investigator should also provide the IRB with a copy of the IB or product labeling, information to be provided to subjects, and any updates. The investigator should provide the IRB with reports, updates, and other information (e.g., expedited safety reports, amendments, and administrative letters) according to regulatory requirements or institution procedures.

### 11.3 INSTITUTIONAL BIOSAFETY COMMITTEE (IBC)

This protocol and any accompanying material provided to the subject (such as subject information sheets, ICF, or descriptions of the study used to obtain informed consent) will be submitted by the investigator to a legally constituted and chartered IBC. Additional materials, such as the IB, will be submitted to the IBC according to the specific Committee and federal (NIH) requirements. Each site will be approved by the IBC in accordance with local procedures and country-specific regulatory requirements. Documentation of IBC approval must be in place prior to drug shipment to the site.

At the discretion of the specific IBC and within federal requirements, IBC oversight of individual sites may be terminated provided (1) all subjects at that site have completed dosing by at least 28 days, and (2) all investigational materials have been fully accounted for and either returned to BNI, destroyed on site, or shipped to a duly licensed destruction facility and a shipping and inventory reconciliation records have been filed in the Pharmacy Manual.

#### **11.4 INFORMED CONSENT**

The ICF and process must comply with the US regulations (§ 21 CFR Part 50), as well as state and local laws. The ICF will document the study-specific information the Investigator or his/her designee provides to the subject and the subject's agreement to participate.

The Investigator, or designee (designee must be listed on the Delegation of Authority log), must explain in terms understandable to the subject the purpose and nature of the study, study procedures, anticipated benefits, potential risks, possible adverse effects, and any discomfort participation in the study may entail. Investigators must ensure that subjects are clearly and fully informed about the purpose, potential risks, and other critical issues regarding clinical studies in which they volunteer to participate. Freely given written informed consent must be obtained from every subject before clinical study participation, including informed consent for any screening procedures conducted to establish subject eligibility for the study. This process must be documented in the subject's source record. Each subject must provide a signed and dated informed consent before any study-related (nonstandard of care) activities are performed. The original and any amended signed and dated consent forms must remain in each subject's study file at the study site and be available for verification by study monitors at any time. A copy of each signed consent form must be given to the subject at the time that it is signed by the subject.

The rights, safety, and well-being of the study subjects are the most important considerations and should prevail over interests of science and society.

#### **11.5 COMPLIANCE WITH THE PROTOCOL**

A complete list of Investigator responsibilities are outlined in the clinical trial research agreement and the Statement of Investigator FDA Form 1572, both of which are signed by the Investigator before commencement of the study. In summary, the Investigator will conduct the study according to the current protocol; will read and understand the IB; will obtain IRB approval to conduct the study; will obtain informed consent from each study participant; will maintain and supply to the Sponsor or designee, auditors and regulatory agencies adequate and accurate records of study activity and drug accountability for study-related monitoring, audits, IRB reviews and regulatory inspections; will report SAEs to the Sponsor or designee and IRB according to the specifics outlined in this protocol; will personally conduct or supervise the study; and will ensure that colleagues participating in the study are informed about their obligations in meeting the above commitments.

## 11.6 RECORDS RETENTION

The Investigator must keep a record that lists all subjects considered for enrollment (including those who signed consent but were not enrolled) in the study. For those subjects subsequently excluded from enrollment, the reason(s) for exclusion is to be recorded.

The Investigator/study staff must maintain adequate and accurate records to enable the conduct of the study to be fully documented and the study data to be subsequently verified. Essential documentation includes, but is not limited to, the Investigator Brochure, signed protocols and amendments, IRB approval letters (dated), signed FDA Form 1572 and Financial Disclosures, signed ICFs (including subject confidentiality information), drug dispensing and accountability records, shipping records of investigational product and study-related materials, signed (electronically), dated and completed CRFs, and documentation of CRF corrections, SAE forms transmitted to BNI or designee and notification of SAEs and related reports, source documentation, normal laboratory values, decoding procedures for blinded studies, curricula vitae for study staff, and all relevant correspondence and other documents pertaining to the conduct of the study.

All essential documentation will be retained by the Investigator for at least 2 years after the date the last marketing application is approved for the drug for the indication for which it is being investigated and until there are no pending or contemplated marketing applications; or, if no application is to be filed or if the application is not approved for such indication, until 2 years after formal discontinuation of clinical development of the drug.

